### **6.5.9 Study drug discontinuation**

Treatment can be terminated at any time, at the discretion of the investigator or the Sponsor, or at the patient's request, in the event of an AE or due to treatment failure.

Study drug treatment has to be discontinued in the following cases during treatment period:

- Occurrence of overt diabetes mellitus; defined as fasting blood glucose  $\geq 126$  mg/dl or  $\geq 7.0$  mmol/l and abnormal findings in OGTT defined by  $\geq 200$  mg/dl or  $\geq 11.1$  mmol/l after 120 minutes. For further instruction see appendix
- Requirement of an increase of the recommended dose to obtain increased growth velocity
- Renal transplantation
- Diagnosis of benign intracranial hypertension
- Malignancy
- Pregnancy
- Withdrawal of informed consent
- Treatment failure

Treatment failure is defined as: Inadequate response to treatment, e.g. height velocity standard deviation score (HVSDS) below +1 in the first year.

Furthermore a standardized controlled procedure for the calculation of the treatment response (via "Treatment Response Control Fax") was implemented (see also 6.5.3 treatment duration) to ensure a unified flawless computation and to authorize treatment continuation, if applicable (managed by Data Management at Metronomia). In case the Investigator does not agree with the assessment by Data Management, Sandoz is informed and initiates the re-assessment of the treatment response data via an independent specialist reader.

Patients who are withdrawn from the study before completing at least one year of treatment with Omnitrope® will be replaced.

Study drug must be discontinued if the investigator concludes that continuation would result in significant safety risk for that patient and in the event of pregnancy.

Patients who discontinue study drug before completing the study should not be considered withdrawn from the study and should be scheduled for a final visit as soon as possible, at which time all of the assessments for the final visit will be performed.

A Study Drug Discontinuation form should be completed, giving the date and reason for stopping the study drug. All patients who discontinue study drug, including those who refuse to return for a final visit, will be contacted for safety evaluations during the 4 weeks following the last dose of the study drug.

Patients who discontinued this study for any reason will not be able to re-enter the study.

#### **6.5.10 Premature patient withdrawal**

Patients *may* voluntarily withdraw from the study or be dropped from it at the discretion of the investigator at any time. Patients should also be withdrawn at any time if the investigator concludes that it would be in the patient's best interest. Patients *must* be withdrawn from the study if any of the following occur:

- Withdrawal of informed consent

Protocol violations should not lead to patient withdrawal unless they indicate a significant risk to the patient's safety. Patients may be considered withdrawn if they state an intention to withdraw, or fail to return for visits, or become lost to follow-up for any reason.

A patient is considered to be lost to follow up in case patient status is unclear because they fail to appear for study visit within visit window without stating an intention to withdraw and the patient does not react to at least three attempts of the investigator to schedule the visit within visit window (the investigator should show "due diligence" by documenting in the source documents steps taken to contact the patient, e.g. dates of telephone calls, registered letters, etc.)

A patient who does not attend the visit during visit window is considered as lost to follow up, unless

- (s)he experiences medical condition, which prevents her/him from appearing to the visit within visit window and
- patient notifies the investigator about this condition during visit window or earlier and
- before or during visit window sponsor grants upfront written approval for the visit outside of visit window.

If premature withdrawal occurs for any reason, the investigator must determine the primary reason for the patient's premature withdrawal from the study and record this information on the CRF. For lost to follow up patients the termination fax specifying the reason of withdrawal should be provided to DM within 4 weeks of calculated visit date.

#### **6.5.11 Emergency unblinding of treatment assignments**

Not applicable.

## 6.6 Contraception measures

Females of child-bearing potential are defined as all females physiologically capable of becoming pregnant. This includes female pediatric patients who are menarchal or who become menarchal during the study.

All menarchal girls and their parents/caregivers should be informed about the potential risks of pregnancy and the need to prevent pregnancy during the study. It is important to be sensitive in introducing this issue, as understanding and comprehension of puberty, sexual activity, pregnancy and contraception is influenced by age, as well as factors such as precocity, socio(educational) economic and familial background. These discussions with the patient and her parents/caregivers are therefore best performed by investigators familiar with the pediatric subject and her family and should be guided by requirements of the local regulatory authorities. These discussions should take into account the socio-economic, cultural factors and religious beliefs of the adolescent participant and her family. The investigator should also discuss the management of the pregnancy test results with the patient and her parents/caregivers. The privacy of the patient should be considered in accordance with the local law and ethics.

Urine pregnancy tests will be performed for all females of child-bearing potential according to the schedule in the Flow Chart. Additional pregnancy tests may be performed at the investigator's discretion during the study. Patients becoming pregnant must be discontinued from study drug.

All female patients of child-bearing potential, defined as all women physiologically capable of becoming pregnant must use effective methods of contraception during dosing of study treatment. Effective contraception methods include:

- Total abstinence (when this is in line with the preferred and usual lifestyle of the subject. Periodic abstinence (e.g., calendar, ovulation, symptothermal, post-ovulation methods) and withdrawal are not acceptable methods of contraception
- Female sterilization (have had surgical bilateral oophorectomy with or without hysterectomy), total hysterectomy or tubal ligation. In case of oophorectomy alone, only when the reproductive status of the woman has been confirmed by follow up hormone level assessment
- Male sterilization. For female subjects participating in the study, the vasectomized male partner must be the sole partner for that subject
- Barrier methods of contraception: Condom or Occlusive cap (diaphragm or cervical/vault caps) with spermicidal foam/gel/film/cream/ vaginal suppository
- Use of oral, injected or implanted hormonal methods of contraception or other forms of hormonal contraception that have comparable efficacy (failure rate <1%), for example hormone vaginal ring or transdermal hormone contraception
- Placement of an intrauterine device (IUD) or intrauterine system (IUS)

In case of use of oral contraception it is recommended that the female patients of childbearing potential is exerting abstinence for a period of 3 months until safe onset of action of the oral contraception.

## 7 Visit Schedule and assessments

The Flow Chart (synopsis) lists assessments and indicates with an “X” the visits during which they are performed. Patients should be seen for all visits at the designated time-point or as close to it as possible. A time window for the visits of up to +/- three weeks will be allowed.

All data obtained from the assessments listed in the Flow-Chart and described in detail in the subsections below must be supported in the patient’s source documentation.

The study visit schedule consists of screening period for up to 8 weeks prior to the initiation of therapy followed by an open treatment period until final height is reached. The study plan timetable (please refer to the Flow Chart Treatment Period) indicates the number and timing of the planned visits. During these visits, the mentioned efficacy and safety parameters will be assessed. It is important to maintain the visit schedule during the treatment period as accurately as possible. If any individual visit date does not conform to the planned schedule, the subsequent visit should be realigned to maintain the schedule relative to the start of the treatment period.

The clinical and laboratory investigational plan per visit is summarized in the Flow Chart Treatment Period.

### 7.1 Procedures by visits

#### 7.1.1 Screening Period (Visit 00)

At the screening visit (to be performed within 8 weeks prior to visit 1), all data to confirm the diagnosis SGA will be collected in addition to demographic and baseline data to determine the patient’s eligibility for study participation.

- Demographics (date of birth, sex, ethnic origin)
- Medical and surgical history
- Prenatal history
  - Placental dysfunction (eclampsia, infarcts), genetic causes
  - Maternal disease
  - Gestational age
  - Birth history
    - Vaginal/caesarean, Apgar-score, blood pH, body weight, body length, neonatal complications (need for glucose, respiratory support)
  - Infant growth data
    - Retrospective weight, length, feeding mode
  - Pre-treatment growth data
    - Height measurement between 18 months and 6 months prior to the start of Omnitrope® treatment to enable calculation of pre-treatment height velocity
    - Current standing height
  - Physical examination, puberty stage and vital signs

- Body mass index
- Parental height and weight
- Growth hormone secretion
  - Collection of historical data with regard to growth hormone secretion
- Written informed consent will be obtained before any measurements are made.
- Recording of patient's and parents' data in the respective CRF
- Patients history and details of concomitant medications
- Recording of historical X-ray radiograph of the patient's left hand and wrist

### 7.1.2 Start of Treatment (Visit 01)

The following investigations and assessments will be performed during clinical examination:

- Physical examination including height, body weight and pubertal status
- Vital signs (blood pressure and heart rate)
- Blood sampling for laboratory testing: Haematology and clinical chemistry including thyroid function, fasting plasma glucose and fasting plasma insulin
- Blood sampling for anti-hGH antibodies, IGF-I and IGFBP-3 determination
- OGTT
- Urinary analysis (dip stick)
- [REDACTED]
- Concomitant medication recording
- Adverse Events recording
- Drug dispensing and recording

At this visit, patients/parents will be carefully instructed by the investigator/clinical staff on the use of the pen injector, the pen needle, and the appropriate injection technique including cleaning of the injection site and discharging of the used needle. The first injection of Omnitrope® will be administered. Patients will receive a three months supply of study drug packed in a cool box and will be instructed to place the study medication in the refrigerator at home as soon as possible. The dispensed study drug will also be recorded in the Drug Accountability Form.

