## 5 Population

The study population will consist of a representative group of children of both sexes, aged  $\geq 4$ , with short stature born small for gestational age (SGA).

SGA is defined as per the label indication authorised by the EMEA:

“Growth disturbance (current height standard deviation score (SDS)  $< -2.5$  and parental adjusted SDS  $< -1$ ) in short children born small for gestational age (SGA), with a birth weight and/or length below -2 standard deviation (SD), who failed to show catch-up growth (height velocity (HV) SDS  $< 0$  during the last year) by 4 years of age or later.”

Standardized and controlled Enrolment Authorization:

To assist Investigators to avoid errors in the local calculation of the auxological parameters by applying different ways of calculation and to ensure that only patients in strict adherence to the SGA definition in the study protocol are enrolled, a standardized and controlled procedure for patient enrolment authorization (“Enrolment Authorization Fax”) was implemented after the first 60 patients were enrolled in the study (by November 2008).

For the patients enrolled before implementation of the “Enrolment Authorization Fax” a standardized approach for the recalculation of growth indication for inclusion according to inclusion criteria 2, 3 and 5 was implemented in March 2009.

Historical data will be used to screen the subjects for eligibility, i.e. records of birth length and weight, as well as height and weight measurements taken 1 year (between 18 months and 6 months) before the start of GH treatment for calculation of HVSDS. For the evaluation of gestational age, the date of the last menstrual period will be used, however, if this is not known, ultrasonographic data obtained during the pregnancy may be used.

The study will be performed in approximately 40 centres in Europe. The treating physicians shall be appropriately qualified and experienced in the diagnosis and management of SGA. The patients will be treated as out-patients.

[REDACTED] Subjects dropping out before completing 1 year of treatment will be replaced.

[REDACTED]

[REDACTED]

[REDACTED]

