### 5.1.2 Exclusion criteria

1. Onset of puberty
2. Closed epiphyses
3. Diabetes type I or type II
4. Fasting blood glucose  $\geq 100$  mg/dl or  $\geq 5.6$  mmol/l measured in venous blood sample
5. Abnormal findings in OGTT defined by  $\geq 140$  mg/dl or  $\geq 7.8$  mmol/l after 120 minutes
6. Known IGF-I level above +2SD for sex and age
7. Acute critical illness e.g. suffering complications following open heart surgery, abdominal surgery, multiple accidental trauma, acute respiratory failure.
8. Known to be hepatitis B or hepatitis C positive or HIV-positive, known to have advanced diseases such as AIDS or tuberculosis

9. Any other disease, genetic disorder or malformation or treatment known to be associated with growth retardation, e.g. Turner or Noonan syndrome, Laron syndrome, Russell-Silver syndrome, Prader-Willi syndrome, skeletal dysplasias, chronic renal failure, cystic fibrosis, heart and liver diseases, malabsorption (coeliac disease), malnutrition, patients receiving radiation therapy of head or spinal cord
10. History of malignancy of any organ system, treated or untreated, within the past 5 years whether or not there is evidence of local recurrence or metastases, with the exception of localized basal cell carcinoma of the skin
11. Known or suspected hypersensitivity to hGH or any of the excipients (benzyl alcohol)
12. Previous treatment with any hGH preparation
13. Oral, inhalative or parenteral treatment with glucocorticoids, except for physiological replacement, or hypothyroidism which has been left untreated, or was inadequately treated, or treated for less than 3 months
14. Treatment with LHRH / gonadotropin releasing hormone (GnRH) analogs (e.g. triptorelin)
15. Treatment with antidiabetic medication (e.g. metformin, insulin)
16. Drug, substance, or alcohol abuse
17. Known to be immunocompromised
18. Intake of growth promoting medication, e.g. anabolic steroids
19. Use of other investigational drugs within 30 days of enrolment
20. Patients unwilling and/or parents/guardians who are not capable of ensuring compliance with the provisions of the study protocol

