## 4 Statistical analyses

### 4.1 General considerations

#### Baseline visit

In principal, Visit V01 (start) is regarded as baseline visit. For some patients only a screening visit, but no baseline visit was performed. For these patients screening visit will be used as baseline visits.

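### Eligibility glucose and OGTT results are first scheduled at the visit that gives the first injection, and the diabetes tables do not separate findings made before treatment from those made during it

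*Protocol*

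**What the plan says.** Protocol 5.1.2 excludes a child whose fasting glucose is at or above 100 mg/dl, or 5.6 "mmol/l measured in venous blood sample" (criterion 4). It also excludes "Abnormal findings in OGTT defined by" a 120-minute value of at least 140 mg/dl or 7.8 mmol/l (criterion 5).

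Protocol 7.1.1 gives the screening visit the task of collecting "demographic and baseline data to determine the patient’s eligibility for study participation". Its procedure list contains history, growth data, examination and consent, but no blood sample and no OGTT. The flow chart agrees: the Screening column is empty for blood chemistry (which includes HbA1c, fasting glucose and insulin) and for OGTT, and the first entry for each is under Start.

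Protocol 7.1.2 (Visit 01) lists blood sampling for "Haematology and clinical chemistry including thyroid function, fasting plasma glucose and fasting plasma insulin" and an OGTT. It then has three months of drug dispensed, and "The first injection of Omnitrope® will be administered" at the same visit. SAP 4.6.2.2 confirms that baseline glucose, insulin, HbA1c and OGTT belong to the start of treatment.

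SAP 4.1 adds: "For some patients only a screening visit, but no baseline visit was performed". For those children the screening visit serves as baseline.

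**The concern.** A criterion that depends on a laboratory result can keep a child out only if the result is read before the first dose. The documents put test and dose in one visit and do not say which comes first in decision terms. They also do not say what happens if a Visit 01 result meets criterion 4 or 5.

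This is a single-arm study whose primary objective, in Protocol 3.1 and SAP 2.2, is the development of diabetes during treatment. With no control group, the only protection against attributing a pre-existing abnormality to the drug is a clean separation of what was present before the first dose from what appeared after it. If enrolment does not guarantee that separation and the tables do not make it either, the DM, IGT and IFG counts mix the two.

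**Working it through.** The point is one of sequence and counting rules. There is no sample size or power figure in the plan to reproduce.

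**1. When the results become available**

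| Item | Screening (Visit 00) | Visit 01 |
|---|---|---|
| Fasting glucose (criterion 4) | not scheduled | scheduled |
| 2-hour OGTT (criterion 5) | not scheduled | scheduled |
| First injection, three-month supply | none | yes |

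**2. Whether another control closes the gap**

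- The Enrolment Authorization Fax (Protocol 5) concerns growth calculations and the SGA definition. For children enrolled before it existed, the retrospective step was a "recalculation of growth indication for inclusion according to inclusion criteria 2, 3 and 5". Glucose is not mentioned in either.
- Protocol 6.3 provides for a child who does not start treatment, but only records the reason.
- Protocol 6.5.9 and the glucose appendix act at overt-diabetes levels, and the appendix lists impaired fasting glucose with impaired OGTT as ongoing. A child over the exclusion limits but below overt levels is not removed by them.
- Source verification of eligibility (Protocol 9.1) and the deviation table (SAP Table 14.1-16) would record a breach, but do not take the child out of any analysis.

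**3. What the analysis does with such a child**

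The FAS needs one dose. The SAF needs one dose and one post-baseline safety assessment (SAP 2.6). The SAP history shows that the per-protocol set was removed. No defined set therefore excludes a child who was abnormal before dosing.

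SAP 4.6.2.2 treats a child fulfilling any DM criterion as a child with DM, and the footnotes to Tables 14.3-3.7 to 14.3-3.9 work on at least one visit. None of them excludes Visit 01. Take a child with fasting glucose below 7.0 mmol/l and a 2-hour value of 7.8 mmol/l at Visit 01, and 2-hour values below 7.8 at every later visit. As written, Table 14.3-3.8 counts that child as having IGT, although nothing abnormal arose on treatment.

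The thresholds also differ. Criterion 4 starts at 5.6 mmol/l, while the SAP's IFG starts at 6.1 mmol/l. Being over an exclusion limit and already meeting an endpoint definition are therefore two separate classifications.

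**4. Scale, as illustration**

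Inputs: 278 enrolled (Protocol, Study status); 8% IGT before GH in a cited cohort of 79 children (Protocol 1.2.4). Assumption: that share applies to children presenting for this study.

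- 0.08 × 278 = 22.2, about 22 children.
- 8% of 79 is about 6 children. The exact 95% interval for 6/79 is 2.8% to 15.8%, which gives 0.028 × 278 = 7.8 to 0.158 × 278 = 43.9, about 8 to 44 children.
- At an assumed 1%: 0.01 × 278 = 2.8 expected, and the chance of at least one is 1 − 0.99^278 = 0.94.

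These are children whom criterion 5 would have to stop on the day of first dosing.

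**The case against.** The strongest reply is that the sequence can work in practice. Protocol 5.1 already restricts enrolment to children with none of the exclusions. Section 7.1.2 lists sampling and OGTT ahead of dispensing. Visits are preferably in the morning (7.3.1), dosing is in the evening (6.5.1), and local laboratories run the chemistry (7.4.6.1). A result could be back before the injection. This stands, and it limits the point to what the protocol leaves open. It does not remove it, because 7.1.2 places the first injection at the visit itself and nothing tells the site to wait.

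The SAP also has partial safeguards: changes from baseline, shift tables for fasting glucose and HbA1c, listings of glucose and OGTT, a requirement in 4.5 that laboratory DM accord with the AE record, and exclusion of pre-treatment AEs from the summaries. However, the OGTT has no shift table, the shift tables use reference ranges and not the DM, IGT or IFG definitions, and the AE requirement covers DM only.

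A reader might infer several stronger things that the documents do not support:

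- **That ineligible children were in fact dosed.** The documents show that this was possible, not that it happened.
- **That the screening-only children in SAP 4.1 have no pre-dose glucose.** The SAP does not say which tests they had. Only the scheduled test is missing.
- **That IGT at entry goes on to diabetes under treatment.** In the cited cohort IGT was 4% after 6 years of GH, and no child developed diabetes. IGT alone also does not meet the SAP's DM definition.
- **That exclusions 3 and 13 fail in the same way.** Known diabetes can be taken from the history at screening, and criterion 13 does not itself call for a new thyroid test.

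**Conclusion.** The point holds in a limited form. Criteria 4 and 5 rest on results first scheduled at the dosing visit, with no stated requirement to have them before the injection. Children over the limits may have been dosed, and any who were remain in the FAS (and in the SAF once they have a post-baseline safety assessment). The consequence for the primary endpoint is firmer, because it follows from the SAP's own counting rule: a Visit 01 finding is tabulated alongside findings made on treatment.

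The size is not known from the documents. The figure of 22 of 278 (8 to 44 over the interval) rests on borrowing the cited cohort's 8% and describes the load on criterion 5. It should not be read as the number wrongly enrolled, or as a number of diabetes cases.

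It may also be tempting to make the children within the exclusion limits the headline group for diabetes. That would be wrong. A child with IGT before treatment who later meets the DM definition is a new case of diabetes, and leaving such children out would take a higher-risk group out of a diabetogenicity study and bias the incidence downward.

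**What to change.** 1. **Protocol.** Sections 5.1.2, 7.1.1, 7.1.2 and the flow chart must be reconciled on when the eligibility glucose results are to be known relative to the first dose. The last child was enrolled on 29 April 2010, so this cannot change who entered.
2. **SAP 4.5 and 4.6.2.2.** For each of DM, IGT and IFG, count as new-onset only a finding after the first dose in a child who did not already meet that same definition before it. Report pre-dose findings separately.
3. **Tables 14.3-3.7 to 14.3-3.9.** Keep the all-SAF result. Add a breakdown by pre-dose status: within the limits of criteria 4 and 5, over either limit, or no pre-dose result. Do not make the within-limits column the headline for diabetes.
4. **SAP 4.1.** State that a child with no pre-dose glucose or OGTT value, including any who had only a screening visit and no such test, has a missing glycaemic baseline. Show later findings in these children in their own column, since they can neither be confirmed as new-onset nor discarded.

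The cost is one derived variable, extra table columns and slightly smaller new-onset denominators. The tests are already in the visit schedule, so no new data collection is needed.
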